**Validity:**

A convenience sample of 44 patients that have undergone ACL reconstruction will be recruited from Liverpool University Hospitals NHS Foundation Trust to determine the validity of the inline dynamometer versus Iso-ED. Inline dynamometry will be performed by Assessor A and Iso-ED performed by Assessor C (15 years' experience). The order of testing will be randomised to account for fatigue and learning effect. Subjects and assessors will be blinded to the results until all testing is completed.

## **6.2 Primary and Secondary Endpoints/Outcome Measures**

The peak torque for each leg (Force [Newtons] x lever length [metres]) recorded at 60° knee flexion will be used as the primary outcome measure. Pain during testing on a numerical rating scale (NRS) will be used as a secondary outcome measure.

## **6.3 Trial Participants**

### **6.3.1 Overall Description of Trial Participants**

Reliability study: healthy subjects, as defined by the inclusion criteria below, recruited from NHS staff at Liverpool University Hospitals NHS Foundation Trust.

Validity study: patients that have undergone ACL reconstruction surgery, with or without meniscal surgery, at Liverpool University Hospitals NHS Foundation Trust.

### **6.3.2 Inclusion Criteria**

- Participant is willing and able to give informed consent for participation in the study.
- Male or Female, aged 18 years or above.
- No contraindications to maximal force testing (see exclusion criteria).
- For the ACL reconstruction participant cohort: diagnosed with ACL injury that was managed with ACL reconstruction surgery, with or without additional meniscal surgery. If medicated, stable dose of current regular medication for at least 4 weeks prior to study entry.
- For the healthy control participant cohort: no current or previous history of significant lower limb injury, or a history of previous minor injury that is symptomatic at the time

of recruitment. No previous lower limb surgery. No course of medication, whether prescribed or over the counter, other than vitamins and mineral supplements or, for females, oral contraceptives.

### **6.3.3 Exclusion Criteria**

The participant may not enter the study if they are unable to provide written consent to study participation, or there are contraindications to maximal force testing, including the following:

- History of chronic disease or disorder that may put the participants at risk because of participation in the study including non-united fractures, epilepsy, cardiac insufficiency, severe peripheral vascular disease, aneurysms, anticoagulant therapy, recent (<3 months) radiotherapy or chemotherapy, long term steroid use (>3 months), pregnancy, neurological disorders (e.g., Parkinson's disease), skin conditions at point of force testing, severe osteoporosis, malignancy, rheumatoid arthritis.
- Conditions or symptoms that may influence the result of the study, or the participant's ability to participate in the study including pain, limited range of motion, knee effusion, or anaemia.

## **6.4 Study Procedures**

Before testing, all subjects will complete a 10-minute warm up on a stationary bike followed by three trials (50%, 75% and 100% maximal effort) to familiarise themselves with each device and to screen for pain. If pain during testing is deemed intolerable by the subject, no further testing will be performed, and the subject will be excluded from the study. A 10-minute recovery period will be used between testing on devices to avoid fatigue.

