### 5.2 Secondary Objectives

To determine comfort levels for each device during testing, as measured with a numerical rating scale of pain (0-10).

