**Cybex isokinetic dynamometer:**

The testing procedure will be conducted at 60° knee flexion in accordance with the device instructions. Humantrak software will be used to determine peak knee extensor torque.

For both devices, three maximal efforts will be performed on each leg with verbal encouragement to 'push as hard as possible' for five seconds, which is sufficient time to generate peak torque. Subjects will rest for 60-seconds between attempts, monitored with a timer (18). The highest value from the three efforts for each device will be used as the primary outcome for each subject.

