#### **6.4.3 Baseline Assessments**

The following demographics will be recorded routinely at baseline:

Gender, age, weight, height, leg dominance, Tegner activity score (TAS).

Pain at rest, measured by a 0-10 numerical rating scale (NRS), will be recorded before initiation of testing. Lever length and force measurements will be recorded during testing.

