### **6.6 Discontinuation/ Withdrawal of Participants from Study Treatment**

Each participant has the right to withdraw from the study at any time. In addition, the investigator may discontinue a participant from the study at any time if it is considered necessary for any reason including:

- The subject becomes pregnant
- Ineligibility (either arising during the study or retrospectively having been overlooked at screening)
- Significant protocol deviation
- Significant non-compliance with study requirements
- An adverse event which requires discontinuation of the testing procedure or results in an inability to continue to comply with study procedures
- Disease progression which requires discontinuation of the study device or results in inability to continue to comply with study procedures
- Consent withdrawn
- Lost to follow up

Withdrawal from the study will result in exclusion of the data for that participant from analysis. In the healthy participant cohort, withdrawn participants will be replaced unless the withdrawal was due to an adverse event that was directly associated with the testing procedure. The reason for withdrawal will be recorded in the CRF.

If the participant is withdrawn due to an adverse event, the investigator will arrange for follow-up visits or telephone calls until the adverse event has resolved or stabilised.

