#### **9.7 Inclusion in Analysis**

Data included in the analysis is described in section 6.6

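### Participants stopped for intolerable pain drop out of the pain results, so the secondary endpoint is summarised in a group selected on that endpoint (minor)

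*Combined protocol and SAP*

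**What the plan says.** The secondary objective in Section 5.2 is "To determine comfort levels for each device during testing", scored from 0 to 10. Section 6.2 makes this the endpoint: "Pain during testing on a numerical rating scale (NRS) will be used as a secondary outcome measure".

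Section 6.4 has every participant perform "three trials (50%, 75% and 100% maximal effort) to familiarise themselves with each device and to screen for pain". At the test itself, on both devices, "three maximal efforts will be performed on each leg". If the participant judges the pain intolerable, "no further testing will be performed, and the subject will be excluded from the study". No score defines intolerable; it is the participant's own judgement.

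On analysis, Section 9.7 says only: "Data included in the analysis is described in section 6.6". Section 6.6 says: "Withdrawal from the study will result in exclusion of the data for that participant from analysis". It makes no exception for the pain score. Section 9.1 covers reliability and validity of torque and gives no method or analysis set for pain.

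On data collection, Section 6.4.3 schedules a pain score at rest before testing and then says: "Lever length and force measurements will be recorded during testing". No section provides for a pain score at the moment a participant is stopped.

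**The concern.** Whether a participant appears in the pain results depends on the pain outcome itself. Intolerable pain on a device is the most informative comfort result the study can produce, and the plan neither analyses it nor counts it by device. In the validity cohort, a patient who tolerates the first device but not the second loses the scores for both.

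Two things are at stake. Pain on each device would tend to be understated, in either cohort. If the two devices are also compared, which is possible only in the validity cohort, the difference may be distorted in a direction that cannot be known beforehand. A score that is not recorded at the stop cannot be reliably recovered later.

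**Working it through.** The plan gives no figure to reproduce, so the check has two parts.

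**1. Following the text.** Section 6.4 speaks of exclusion and Section 6.6 of withdrawal, so there are two readings of a stop for pain.
- *Stop read as a withdrawal.* The nearest item in Section 6.6 is an adverse event that ends the testing procedure. The participant's data then leave the analysis.
- *Stop read as a screen failure.* The participant never enters the analysis.

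On both readings the participant is missing from the pain results. The screening reading does not remove the selection, because familiarisation uses the study devices at up to 100% effort. Nor does it cover a stop during the test efforts.

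Three other provisions were checked. Section 6.6 records why someone withdrew, Section 8.1 records whether an adverse event was device-related, and Section 9.5 promises that all data will be presented, with raw data attached. These allow disclosure. None returns a stopped participant to the pain results or requires counts by device.

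**2. Illustrating the size.** From the documents: 44 validity participants, made up of 40 plus an attrition allowance of 4 (Section 9.2), and a 0-10 scale. Everything else is assumed: means, SDs, the correlation between devices, and the score at which pain becomes intolerable. Pairs of correlated scores were drawn, rounded and clipped to 0-10, and a pair was dropped if either score reached the cut-off.

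If a proportion p is stopped, then for each device

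mean(all) - mean(kept) = p × [mean(stopped) - mean(kept)],

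and the between-device difference moves by -p × (gap for device 1 - gap for device 2), where each gap is the term in square brackets.

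Take means 3 v 2, both SDs 2, correlation 0.6 and cut-off 7, with p = 4.7%:
- Device 1 falls from 3.06 to 2.86, by 0.20. The implied gap is 0.20/0.047 = 4.3.
- Device 2 falls from 2.16 to 2.02, by 0.14. The implied gap is 0.14/0.047 = 3.0.
- The difference moves by -0.047 × (4.3 - 3.0) = -0.06, from 0.90 to 0.84.

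The two gaps depend on the spread on each device, so the direction is not fixed. Other settings with correlation 0.6:

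| Assumed means | SDs | Cut-off | Stopped | Difference, all to kept |
|---|---|---|---|---|
| 4 v 2 | 2.5, 2.5 | 8 | 8.7% | 1.76 to 1.60 |
| 4 v 4 | 2.5, 1.5 | 8 | 8.5% | 0.05 to -0.19 |
| 4 v 3.5 | 1.5, 2.5 | 8 | 6.0% | 0.42 to 0.59 |
| 3 v 2 | 1.5, 2.5 | 7 | 4.2% | 0.71 to 0.83 |
| 3 v 2 | 2.5, 1.5 | 7 | 8.1% | 1.08 to 0.82 |

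A wider grid of 1,620 settings used means 1-5 and 1-4, SDs 1.5, 2 or 2.5 on each device, correlation 0.3, 0.6 or 0.8, and a cut-off of 7, 8 or varying by person from 6 to 9. Neither device mean rose in any setting.

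| Proportion stopped | Fall in each device mean | Movement of the difference |
|---|---|---|
| At most 5% (0.05 × 44 = 2.2 people) | 0 to 0.23 | -0.17 to +0.17 |
| At most 10% (0.10 × 44 = 4.4 people) | 0 to 0.46 | -0.34 to +0.34 |

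In the 1,058 settings with at most 10% stopped, the absolute difference widened by more than 0.02 in none of those with equal SDs and in 21% of those with unequal SDs. It shrank by more than 0.02 in 55% of each. These are shares of assumed settings, not probabilities.

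With mild pain (2 v 1, SD 1.5), at most 0.1% are stopped and nothing changes by more than 0.01. The grid reaches 36% stopped, but that fits poorly with the entry criteria and the 10% attrition allowance.

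**The case against.** The strongest reply is that this is largely a matter of defining the population. Familiarisation is described as a pain screen, Section 6.3.3 already excludes people whose pain may affect results or participation, and comfort among people able to do maximal testing is a legitimate target. That is fair for stops during familiarisation if the target is declared, which it is not. It does not cover stops during the test efforts.

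Second, Section 9.1 specifies no pain summary at all, and the link from exclusion in 6.4 to withdrawal in 6.6 is never stated outright. Both points are correct. What is said here about the summary describes what the only stated inclusion rule produces by default. Even a plain mean per device would carry the selection.

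Third, Section 9.5 may let a reader find the stopped cases, and silence about a test-time pain score under the heading of baseline assessments is weak evidence that none would be taken. Granted. But disclosure does not put these people into the analysis, and counts by device are not assured.

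Fourth, the size is assumed throughout and may be trivial. Patients are already booked for isokinetic dynamometry (Section 6.4.2), although that says nothing about tolerance of the inline device. With an SD of 2, the standard error of a mean in 44 people is 2/√44 = 0.30, larger than the shift at 5% stopped. This supports a minor rating.

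Finally, the remedy is partial. If all stops occur at maximal effort, keeping the scores restores most of each device mean but only about half of the loss in the paired difference (in one setting 0.84 rises to 0.87 against a true 0.90; in another 1.60 rises to 1.68 against 1.75), because the second device is never attempted.

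**Conclusion.** The concern holds and is minor. Followed as written, Sections 6.4, 6.6 and 9.7 select the pain results on the pain outcome. The conclusion about direction is firm for each device separately: pain tends to be understated. For the between-device difference the direction is unknown. It tends to shrink when the spreads are similar and may shift or widen when they are not.

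The amount cannot be determined from the documents. It could be close to zero, and under the assumed settings it reaches at most about a quarter of a point per device mean if 2 of 44 are stopped and about half a point if 4 of 44 are. Confidence is medium, because the plan is silent on how pain is to be summarised. The primary torque analyses are not touched by this point.

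**What to change.** Leave the stopping rule as it is and change the data handling:

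1. In Sections 6.6 and 9.7, state that a participant stopped for pain is left out of the torque analyses only. Keep the pain data for the secondary endpoint unless consent was withdrawn or the participant was ineligible for another reason.
2. Record the pain score for each device attempted, including at a stop, with the device, leg and effort level (50%, 75% or 100% familiarisation, or test effort).
3. Beside the pain summaries, report the number stopped for pain by device and by test order, among those who attempted each device.

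Do not pool scores from submaximal familiarisation stops with maximal-effort scores, except in a labelled sensitivity analysis. The counts in item 3 carry the information from those stops. A mixed model, a worst-rank score or a comparison restricted to the first device tested is optional.

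The cost is a little more SAP and CRF wording and a few extra pain entries. The drawback is that some participants will have pain data on one device only, and scores at submaximal stops will need to be shown separately.

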### **Inline dynamometer – KForce Link (capacity 300kg):**

The subject will be sat on the end of a sturdy plinth with a small foam pad placed under the distal thigh for comfort. Ankle straps with double D-rings (Vorcool) will be securely attached directly above the malleoli, with one end of the dynamometer connected to the D-rings via a snap hook. Using a goniometer, the knee will be positioned in 60° knee flexion and the inline dynamometer aligned perpendicular to the leg by adjusting the height of the plinth and the inelastic strap, which anchors the dynamometer to the plinth. The subject will be instructed to maintain the trunk in an upright position, using their hands on the side of the plinth for stability. The dynamometer will be 'zeroed' with the knees relaxed at right angles before each trial. Lever length will be recorded in metres with a tape measure, using the lateral epicondyle of the femur and middle of the ankle strap as reference points.

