To date, only one study has investigated the reliability and validity of HHD for measuring peak knee extensor torque in patients following ACLR (17). 'Push-type' HHD performed isometrically at 90° knee flexion was shown to have excellent test-retest reliability (ICC: 0.98) and 100% specificity for detecting a limb symmetry index (LSI) >10%, but only moderate to good validity ( $r=0.62$ ) versus isokinetic dynamometry. Although LSI is recommended as an objective, criterion-based guideline for return to running (18) or RTP (2) following ACLR, leg dominance or dysfunction of the reference limb may overestimate the capacity of the side being measured, potentially leading to a premature return to high-risk activities and subsequent re-injury (19). Peak isometric knee extensor torque normalised to body weight is an alternative means of determining whether an individual has achieved target values associated with positive knee-joint function following ACLR ( $\geq 3.0-3.1$  Nm/kg) (20, 21). Mean peak torque values in the aforementioned study were 1.67 ( $\pm 7.4$ ) Nm/kg and 2.03 ( $\pm 7.9$ ) Nm/kg for isometric HHD and isokinetic testing respectively, indicating a lower force generating capacity for 'push-type' HHD. In addition, since the reference values were

obtained isokinetically (60°/sec), it is likely that the validity of 'push-type' HHD would be lower if Iso-ED was used as the reference standard.

Inline dynamometers allow isometric knee extensor torque to be measured at peak angles (i.e., 60-70°), but the reliability and validity of this 'pull-type' dynamometry has not been adequately evaluated (10, 22). The objective of this study therefore is to determine the reliability and validity of inline 'pull-type' dynamometry for measuring peak isometric knee extensor torque in patients following ACLR. We hypothesise that inline dynamometry is a reliable and valid measure of peak isometric knee extensor torque when performed at 60-70° knee flexion, using Iso-ED as the gold-standard reference.

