## **9. STATISTICS**

### **9.1 Description of Statistical Methods**

Inter and test-retest reliability will be calculated using intra-class correlation coefficients (ICC) with 95% confidence intervals (CI) and illustrated using a Bland & Altman plot. Standard error of measurement (SEM =  $[SD\sqrt{1-ICC}]$ ) and the minimal detectable change (MDC) ( $1.96 \times \sqrt{2} \times SEM$ ) will be calculated to verify the absolute error of the instrument and the smallest change considered significant respectively.

ICC values will be considered as follows: < 0.69: weak reliability, 0.70–0.79 reasonable reliability, 0.80–0.89 good reliability, and 0.90–1.0 excellent reliability

Validity will be calculated using ICC (95% CI), Pearson product moment correlation (Pearson-r) and illustrated using Bland & Altman plot.

Pearson values of coefficients will be established as follows: < 0.5 indicated weak validity, 0.5–0.75 indicated moderate to good validity, and > 0.75 indicated excellent validity.

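### Inline torque has no term for the gravity moment of the lower leg and the Cybex gravity setting is unstated, so the validity comparison may carry an offset of about 3–9 Nm

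*Combined protocol and SAP*

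**What the plan says.** For the inline device, section 6.4 gives the zero position: "The dynamometer will be 'zeroed' with the knees relaxed at right angles before each trial". For the test itself, "the knee will be positioned in 60° knee flexion and the inline dynamometer aligned perpendicular to the leg". The gauge is held by "the inelastic strap, which anchors the dynamometer to the plinth", and lever length is taped "using the lateral epicondyle of the femur and middle of the ankle strap as reference points".

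Section 6.2 defines the primary outcome: "The peak torque for each leg (Force [Newtons] x lever length [metres]) recorded at 60° knee flexion". Neither section weighs the limb or adds a limb-weight term to the inline value.

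For the reference device, section 6.4 says: "The testing procedure will be conducted at 60° knee flexion in accordance with the device instructions". Gravity correction is neither required nor excluded.

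Section 9.1 gives the analysis: "Validity will be calculated using ICC (95% CI), Pearson product moment correlation (Pearson-r) and illustrated using Bland & Altman plot". The form of the ICC is not stated.

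**The concern.** With the knee at 60° and the thigh about horizontal, the lower leg is held about 30° forward of vertical. Its weight then produces a flexion moment, which the quadriceps must overcome before any tension reaches the gauge. Force times lever length recovers only what is left over, yet sections 5.1 and 6.2 treat the result as knee extensor torque.

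The validity study asks whether two devices give the same torque. The plan fixes the inline device to net torque and leaves the Cybex basis open. A difference in gravity convention could then be read as a difference between instruments. Randomised test order and blinding do not remove a systematic offset, and more patients would only estimate it more precisely. Section 4 shows how such a gap might be read: it takes a lower mean on a push-type device (1.67 against 2.03 Nm/kg) as a sign that the method draws out less force.

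**Working it through.** The documents give no figure for limb weight or gravity correction, so there is none to reproduce.

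**Step 1. Moment balance.** Let F be the gauge force, L the lever length, m the mass of shank plus foot, d the distance of its centre of mass from the knee, and g = 9.81 m/s². With the thigh horizontal:

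F × L = muscle torque − m × g × d × sin(90° − flexion angle)

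- At 90° flexion the gravity term is m × g × d × sin 0° = 0.
- At 60° it is m × g × d × sin 30° = 0.5 × m × g × d.

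**Step 2. Does the zero angle matter?** The strap resists extension and carries tension only. A relaxed leg does not load it, whether at 90° or at 60°. Zeroing at 60° would also read zero and leave every torque unchanged. The shortfall comes from the formula in section 6.2.

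**Step 3. Size.** Assumptions, none from the documents: shank plus foot 5–6.5% of body mass, d = 0.20–0.28 m, body mass 60–100 kg.

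- Low: 0.05 × 60 × 9.81 × 0.20 × 0.5 = 2.9 Nm (0.049 Nm/kg)
- Middle: 0.061 × 80 × 9.81 × 0.25 × 0.5 = 6.0 Nm (0.075 Nm/kg)
- High: 0.065 × 100 × 9.81 × 0.28 × 0.5 = 8.9 Nm (0.089 Nm/kg)

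Taking 7% as the upper mass fraction raises the high case to 0.07 × 100 × 9.81 × 0.28 × 0.5 = 9.6 Nm. For scale only, 0.049–0.089 Nm/kg is 2.9–5.3% of 1.67 and 2.4–4.4% of 2.03 Nm/kg, the means quoted in section 4.

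**Step 4. Effect on the planned statistics if the Cybex is corrected.** I simulated 400,000 pairs with body mass mean 80 kg (SD 13), torque mean 2.3 Nm/kg and independent random error in each device. The middle-case term was then subtracted from the inline value. Mean torque was about 184 Nm. The half-width is that of the 95% CI for the mean difference with 44 pairs, one per patient.

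| Torque CV | Error SD (Nm) | Pearson r | Absolute-agreement ICC | Consistency ICC | Mean difference (Nm) | Half-width (Nm) |
|---|---|---|---|---|---|---|
| 25% | 8 | 0.9795 → 0.9792 | 0.9795 → 0.9735 | 0.9795 → 0.9791 | −5.97 | 3.45 |
| 25% | 15 | 0.9314 → 0.9307 | 0.9314 → 0.9256 | 0.9314 → 0.9307 | −5.97 | 6.45 |
| 35% | 8 | 0.9875 → 0.9873 | 0.9875 → 0.9839 | 0.9875 → 0.9873 | −5.99 | 3.46 |
| 35% | 15 | 0.9574 → 0.9571 | 0.9574 → 0.9539 | 0.9574 → 0.9571 | −5.95 | 6.44 |

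Each arrow runs from no offset to offset. The bias of about 6 Nm exceeds the half-width when random error is small and falls just short of it when error is larger.

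**Step 5. Reliability.** The inter-rater and test-retest comparisons use the inline device on the same legs at the same angle. Both readings lack essentially the same term, so it drops out of the difference.

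**Step 6. If the Cybex is uncorrected.** Both devices report net torque, and the term largely cancels in the comparison.

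**The case against.** The strongest reply is that little of this is established and less of it matters. The offset between devices exists only if the Cybex value is gravity-corrected, and the documents do not say that it is. Pearson r and the ICC barely move. In every scenario above they stay in the top band of section 9.1. With 44 pairs the bias may not be distinguishable from zero. If the simple inline method reads low, that is a property of the method, which the Bland-Altman plot ought to show. Correcting it would validate a modelled value and not the one a clinic would use.

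Most of this stands, and it limits the point to a modest, conditional shift. It does not answer the fact that, without a stated Cybex setting, a reader of the plot could not tell a gravity convention from a device fault. Reporting the raw inline value beside the corrected one meets the last objection.

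Three stronger readings are tempting, and the documents do not support them.

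- A reader might infer that zeroing at right angles causes the shortfall. Step 2 shows that it does not, and moving the zero position would fix nothing.
- A reader might infer that the inline device will be wrongly reported as invalid. That needs a corrected Cybex value, which is not established, and the coefficients in section 9.1 would hardly register it.
- A reader might infer that torque will be understated against the 3.0–3.1 Nm/kg target in section 4. Section 9.1 plans no such comparison, and whether those targets were gravity-corrected cannot be seen from the documents.

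The percentages in Step 3 are also only a rough scale. The two means come from push-type testing at 90° and from isokinetic testing, not from isometric testing at 60°.

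**Conclusion.** The concern holds in a limited form. As defined, inline torque is net torque and lies below knee extensor torque by about 6 Nm at 80 kg, or about 3–9 Nm over 60–100 kg. If the Cybex value is gravity-corrected, the Bland-Altman mean difference and limits shift by that amount in one direction. An absolute-agreement ICC falls by about 0.004–0.006 in the scenarios tried, and Pearson r and a consistency ICC are practically unchanged. If the Cybex value is uncorrected, the comparison is largely unaffected, and both devices read net torque.

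The size rests on assumed limb mass and centre of mass and on a horizontal thigh. The foam pad under the distal thigh may alter the 30° angle slightly. The direction does not depend on the exact values. The change is worth making because it bears on the validity objective and costs little. The Cybex setting should be fixed before data collection, since an unrecorded setting may not be recoverable later.

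**What to change.** In section 6.4, state whether the Cybex isometric torque is gravity-corrected, and record the setting for each test. In sections 6.2 and 6.4, say that the primary validity comparison is made with both devices on one gravity basis.

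If the Cybex value is corrected, add the limb-weight moment at 60° to each inline torque before analysis. Take it from the Cybex limb-weight value where available. Otherwise use a prespecified formula based on body weight (recorded under section 6.4.3) and lever length (section 6.4). Report agreement for the raw inline value as well.

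Switching off any Cybex correction would also align the devices. It would alter the reference standard, however, and under section 6.4.2 these patients are already scheduled for Cybex testing.

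The cost is a few sentences and one extra analysis column, with no new test or visit. The formula adds a modelled term with its own error. At 80 kg it runs from 0.05 × 80 × 9.81 × 0.20 × 0.5 = 3.9 Nm to 0.07 × 80 × 9.81 × 0.28 × 0.5 = 7.7 Nm, roughly ±2 Nm. This is a reason to prefer a measured limb weight where there is one.
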